3.2. Number of Subjects

A total of 1,400 study participants will be enrolled, in order to achieve an overall accrual target of 1,200 participants across sites

3.3. Duration of Participation

An individual participant will be seen ranging from a single visit to a maximum of 7 visits (at pre-specified time points) depending on the time they enter the study (Fig 6). The maximum duration of participation for any one participant is 18 months if they enter the study in the first trimester (after the first 8 weeks to allow room for pregnancy confirmation). In addition, the maximum study duration is estimated to be 18 months due to funding/budgetary restrictions. The minimum duration of participation is one visit (1 day) if they enroll after 9 months postpartum and baseline visit is performed on the same day.

3.4. Identification of Source Data

Study-specific case report forms (CRFs) will be used to document demographic and clinical data obtained as part of the study.

All recorded or clinical and demographic data will be stored and shared with the Mayo study team as a limited data set using a secure online REDCap database with password protection. The Coordinating Center will provide individual (staff-specific) usernames and passwords to the electronic REDCap database for the study investigators and research staff at each site in Nigeria. This will help ensure attribution of data and changes to existing data to the individual study staff member. Mayo Clinic servers will be utilized to store the data and will be maintained by study staff. Any data recorded on paper documents will be kept in locked cabinets at participating sites (See Guidance Document on Study Operations and Procedures for details).

The following source data will not be directly collected in the CRFs, but will be collected through the secure file share transfer portal as previously described and integrated into the master database:

- Digital ECG data
- AI-ECG predictions

4. Subject Selection Enrollment and Withdrawal

4.1. Inclusion Criteria

- Adult female age 18 – 49 years
- Currently pregnant or within 12 months postpartum
- Willing and able to provide informed consent

4.2. Exclusion Criteria

- Under 18 years of age
- Complex congenital heart disease (single ventricle physiology or significant shunts with cardiac structural changes)
- Significant conduction abnormalities (ventricular pacing on recorded ECG, pacemaker dependence, or severely abnormal/bizarre QRS morphology on ECG tracings)
- Unable or unwilling to provide consent

4.3. Subject Screening, Recruitment, and Enrollment

Study participants will be enrolled from multiple healthcare institutions in Nigeria, estimated to have the highest incidence of peripartum cardiomyopathy in the world (incidence of 1 in 100 deliveries) (M. B. Davis et al., 2020). No subjects will be enrolled at Mayo Clinic.

All enrolling sites in Nigeria will conduct enrollment at identified clinics or hospitals. All enrolling sites will develop a site-specific recruitment and enrollment plan following local institutional procedures, local regulations and ethics boards requirements.

4.3.1 Screening, Recruitment, and Enrollment Plan

The local site investigator and/or study coordinator will pre-screen potential participants by reviewing medical records of patients already seen or newly identified patients. A study staff member will present the study information to the potential participants during a clinic or hospital encounter. If the participant is interested and willing to consent immediately, then an approved study staff will review the informed consent process with the participant. If the participant needs additional time to think about the study and participation, they will be given a copy of the informed consent form (ICF), and any other related IRB study approved document(s). Study staff will follow up with the potential participant at 1-2 weeks to learn if he/she is still interested and would like to participate. If a potential participant is still interested, a screening visit will be scheduled to review the ICF to obtain signatures required to enroll in the study.

The site Study Coordinator/staff will utilize the steps that follow to screen participants for the study. A detailed operational plan along with templates (i.e., screening logs) is contained in the Study Protocol Manual of Operations.

I. Pre-Screening Phase

- a. Potential participant will be identified during clinic or hospital encounters

II. Screening Phase

- a. Study staff will meet with potential participant to explain the study
- b. Study staff will confirm that participant meets eligibility criteria
- c. Study staff will have the participant sign an Informed Consent Form and provide copies to participant while placing originals in participant file.
- d. Study staff will collect contact information for participant

The study coordinators will be hired and trained locally to present the trial information without bias or pressure and in a culturally appropriate manner. Translators will be used at the local site as needed. Screening and enrollment failures and related reasons for same will be discussed at the monthly review meetings and potential actions will be taken as need. Attention will be paid to adhering to regulatory issues.

4.4. Early Withdrawal of Subjects

4.4.1. When and How to Withdraw Subjects

Participation is strictly voluntary. Participants may withdraw at any point in the study which will not negatively impact future care. Investigators may withdraw participants at any point if they feel it is in the best interest of the participant to do so. Reasons for withdrawal will be documented locally.

4.4.2. Data Collection and Follow-up for Withdrawn Subjects

In the event a participant discontinues study interventions before study completion, every effort will be made by the study team to have the participant continue to complete all other study

procedures. However, if the participant is not willing to continue study participation, the study team will attempt to collect the final visit data.

5. ECG Testing and Echocardiogram Details

5.1. Description

Standard ECGs: The study will provide each participating site with a standard 12-lead ECG machine for use for the study as well as standard operating procedures (SOPs) on how to complete and transmit de-identified electronic ECGs to Mayo Clinic with a study identifier attached to each ECG file. Each site will perform a 12-lead ECG during each participant visit using standard clinical protocols. The ECGs recorded will be stripped of personally identifying and study identifier will be attached to the digital 12-lead ECG file. The ECG file will be exported and transmitted to Mayo Clinic study staff in XML format using the secure Mayo Clinic On-Demand File transfer portal. If the stripping of identifiable information should be missed by the site, Mayo Clinic staff will remove the identifying information, and or treat the data as confidential and will keep the file secure in the Mayo Clinic Research Server where only study staff will have access to it.

Echocardiogram: The coordinating center will cover the costs associated with performing echocardiograms per study protocol among study participants randomized to the intervention arm at each site. Results of the echocardiogram will be documented in REDCap. A repeat echocardiogram will be performed if a subsequent AI-ECG result flags positive cardiomyopathy in the intervention arm (if the baseline echocardiogram was normal). The results from the repeat echocardiograms will also be reported in REDCap. All echocardiograms will be reviewed by the local cardiologist at each site and performed in accordance with the American Society of Echocardiography guidelines for ejection fraction assessment.

Portable point-of-care (POC) ECGs (Eko DUO Stethoscope and AliveCor Kardia Mobile devices): will be recorded simultaneously in the intervention arm based on device manufacturer protocols following training at each site. AliveCor and Eko health will provide the portable ECG recordings taken at the participating sites to Mayo Clinic for analysis by our data engineering/science team. The de-identified data collected under this IRB may be used for future research. Participants in the intervention arm will have a seated wireless AliveCor Kardia Mobile 6-lead ECG (Figure 1) and a supine/seated Eko DUO Digital Stethoscope ECG recorded before or after a standard 12-lead ECG. The duration of patient involvement in the study will include consent review and signature, completion of a standard 12-lead ECG for all participants as well as the portable ECG recordings as described above. All ECG data will be recorded by study coordinators at each site following appropriate training on how to obtain the ECGs. The portable electrocardiographic tracings recorded by both devices are strictly for research purposes as it relates to this study and is not intended for use in guiding the patient's clinical care.

AliveCor Kardia 6L device: This is an FDA approved handheld smart device. This device will be observed for handheld recording as approved by FDA. The ECG signal is communicated wirelessly via Bluetooth to a mobile computing platform (MCP, which is a smartphone or tablet)

running the Kardia application (App). The Kardia App processes the signal into a real-time ECG. The data from Leads I and II are used to calculate, on a mobile or web-based app and in real time, Leads III, aVR, aVL, aVF. The results of the electrocardiographic tracings recorded by the AliveCor devices will not be entered into the electronic medical record or used to guide the patient's clinical care. De-identified data from the recordings will be uploaded to the AliveCor cloud, which is only accessible to the study team by username and password. For individuals unable to record from all three electrodes, data can be acquired from two electrodes only, as shown in Figure 1. The AliveCor recordings will be identifiable by an assigned study ID and date of transmission. Data from the AliveCor device will be transmitted via the research study's smartphone/tablet app to the cloud, where it will be password protected via account log-in, and only accessible to the research team for download to the Mayo research server. The AliveCor cloud server will only be utilized during the duration of the research study and is not accessible to external parties.

Eko DUO Digital Stethoscope: This is an FDA-cleared and CE-marked electronic stethoscope that allows audio recording of heart sound to produce a phonocardiogram (PCG) as well as a single-lead ECG recording. Based on the AI-ECG model for cardiomyopathy detection developed by Attia et. al. (Z. I. Attia et al., 2019), Eko health has developed a single-lead version of the same model to be used with the Eko DUO digital stethoscope which can provide near real-time AI-ECG predictions for cardiomyopathy at the point of care (Zachi I Attia, Jennifer Dugan, et al., 2019). The results of the electrocardiographic tracings recorded by the Eko DUO stethoscope will not be entered into the electronic medical record or used to guide the patient's clinical care. The Eko DUO recordings will be identifiable by an assigned study ID and date of transmission. Raw data from the Eko DUO Stethoscope device will be transmitted via the research study's smartphone/tablet app to the cloud, where it will be password protected via account log-in, and only accessible to the research team for download to the Mayo research server. The Eko DUO cloud server will only be utilized during the duration of the research study and is not accessible to external parties.

Using the AliveCor or Eko DUO device to record electrocardiographic tracings should not cause discomfort or inconvenience other than a minimal delay to acquire the readings. The AliveCor Kardia 6L and Eko Duo are 510(k) cleared devices. Between uses the electrodes and all surfaces will be cleaned using antiseptic (75% alcohol) wipes. Sequential numbers will be used for enrollment de-identification for the portable ECG recordings. Acquired data from each device will be stored on HIPAA-compliant, encrypted servers.

6. Study Procedures

6.1. Schedule of Events

6.1.1 - Control Arm

Assessment	Screening	Baseline, Randomization Visit 1	Visits 2 -7
------------	-----------	---------------------------------------	-------------

Inclusion/Exclusion Criteria	X	X	
Informed Consent ^a		X	
Demographics		X	
Clinical Assessments ^b		X	X
Medical History		X	
New Clinical Diagnosis			X
Current Medications		X	
Blood Chemistries ^c		X	
Hematology ^d		X	
Urine Analysis ^e		X	X
Inclusion/Exclusion Criteria	X	X	
Enrollment/Randomization		X	
12 lead ECG		X	X
AI-ECG – Sex and Age Determination		X	X

^aConsent may be obtained prior to baseline/randomization visit^bHeight, weight, blood pressure and heart rate^cTo be abstracted from medical records – Serum Cr, eGFR^dTo be abstracted from medical records – Hemoglobin (g/dl) or Hematocrit (%) or Packed Cell Volume; Hemoglobin Genotype (Hb AA, AS, SS, Sc); Rhesus factor (negative or positive), infectious screen.^eTo be abstracted from medical records – Positive for proteins (Yes or No)

6.1.2 - Intervention Arm

Assessment	Screening	Baseline, Randomization Visit 1	Visits 2-7
Inclusion/Exclusion Criteria	X	X	
Informed Consent ^a		X	
Demographics		X	
Clinical Assessments ^b		X	X
Medical History		X	
New Clinical Diagnosis			X
Current Medications		X	
Blood Chemistries ^c		X	
Hematology ^d		X	
Urine Analysis ^e		X	X
Enrollment/Randomization		X	
12 lead ECG		X	X
AI-ECG - Sex, Age, and Cardiomyopathy Determination		X	X
Portable ECG ^f		X	X
Echocardiogram ^g *		X	

^aConsent may be obtained prior to baseline/randomization visit^bHeight, weight, blood pressure and heart rate^cTo be abstracted from medical records – Serum Cr, eGFR^dTo be abstracted from medical records – Hemoglobin (g/dl) or Hematocrit (%) or Packed Cell Volume; Hemoglobin Genotype (Hb AA, AS, SS, Sc); Rhesus factor (negative or positive), infectious screen.^eTo be abstracted from medical records – Positive for proteins (Yes or No)^fPortable ECGs will be performed only among those in the intervention arm

^gEchocardiograms will be performed on all participants in the intervention arm at baseline and *if any new subsequent ECGs flag positive based on the AI-ECG predictions for cardiomyopathy (low ejection fraction) provided the baseline echocardiogram was normal. Participants with cardiomyopathy detected at any time point during the study will have a repeat echocardiogram at the end of study participation or 12 months postpartum (whichever is earlier) to assess for left ventricular recovery.

6.2. Visits

All patients will have follow-up and medical record review to ascertain the development of study clinical outcomes. Patients can enter the study at any time point during pregnancy or the postpartum period (up to 12 months after delivery). All women will have a standard 12-lead ECG performed at the time of enrollment and at pre-specified intervals through 12 months postpartum or study end (whichever is earlier). ECGs will be performed up to 7 times during the study period including during each trimester of pregnancy (up to 3 ECGs), between delivery and 6 weeks (1 ECG), between 6 weeks and 3 months (1 ECG), between 3 and 5 months (1 ECG), and between 5 and 12 months postpartum (1 ECG). Only participants in the intervention arm will have a baseline echocardiogram as well as simultaneous portable ECGs recorded with near real-time provision of AI-ECG cardiomyopathy prediction. Additionally, a newly positive AI-ECG screen for cardiomyopathy during any of the 6 visits will trigger an echocardiogram for participants in the intervention arm. This strategy for performing echocardiograms was selected as it is not practical to obtain an echocardiogram during each prenatal care visit due to time, skilled expertise required, and cost. In addition, the negative predictive value of the AI-enabled ECG is known to be very high (consistently exceeding 95%) in multiple internal and external patient populations (D. Adedinsewo et al., 2020; Attia et al., 2021; Z. I. Attia et al., 2019). Patients in the intervention group with cardiomyopathy detected on an echocardiogram will have a repeat echocardiogram performed at the end of the study period (or at 12 months postpartum depending on which is earlier) as part of the study protocol to assess for left ventricular recovery.

All echocardiograms will be reviewed for adherence to the American Society of Echocardiography guidelines for ejection fraction assessment as part of the study. LVEF measurements will be recorded for study participants using REDCap.

6.2.1. Screening

To be conducted as described in section 4 of this protocol

6.2.2. Randomization/Baseline visit

After informed consent has been obtained, the following procedures will be completed per the schedule of events table:

Control Arm

- Enrollment Randomization
- Demographic information
- Clinical Assessments
- Medical history
- Current Medications
- Blood Chemistries
- Hematology
- Urine Analysis
- 12-lead ECG
- AI-ECG Sex & Age Determination

Intervention Arm

- Enrollment Randomization
- Demographic information
- Clinical Assessments
- Medical history
- Current Medications
- Blood Chemistries
- Hematology
- Urine Analysis
- 12-lead ECG
- AI-ECG Sex, Age, & Cardiomyopathy Determination
- Portable ECGs
- Echocardiogram(s)

Visits 2-7**Control Arm**

- New Clinical Diagnosis
- Clinical Assessments
- Current Medications
- Urine Analysis
- 12-lead ECG
- AI-ECG Sex & Age Determination

Intervention Arm

- New Clinical Diagnosis
- Clinical Assessments
- Urine Analysis
- 12-lead ECG
- AI-ECG Sex, Age, & Cardiomyopathy Determination
- Portable ECGs

- Repeat echocardiogram for Positive AI-ECG screen/new cardiomyopathy diagnosis (if baseline echocardiogram was normal)

6.3. Positive AI-ECG Screen/New Cardiomyopathy Diagnosis (Intervention arm only)

In the event that the AI-ECG detects cardiomyopathy (and baseline echocardiogram showed normal ejection fraction), this would trigger an echocardiogram as part of the research study protocol and the results would be reviewed by a local cardiologist and provided to the managing obstetrician which have already been identified at each site. For participants with newly diagnosed cardiomyopathy (confirmed by echocardiography), the decision to initiate guideline directed medical therapy or other treatment will be based on a clinical evaluation by a local cardiologist at each site, local clinical practice standards, treatment options available and patient preferences.

6.4. Age and Sex ECG Estimation

The application of the AI-ECG algorithms to estimate age and sex will occur at the coordinating center. As such, the estimation will be asynchronous with the clinical visits at each sites. The Coordinating Center will process ECGs as they arrive (~ monthly for each site) and return a report back to study investigators with the model results. These results may be communicated to the participant at a subsequent study visit (at the provider's discretion).

7. Statistical Plan

7.1. Sample Size Determination

LVEF<50% is not expected to be diagnosed in the control arm due to the lack of routine echocardiograms, but for sample size calculations, we have assumed that 1% will be diagnosed based on literature derived incidence rate of 1 in 100 deliveries (M. B. Davis et al., 2020). With the AI-ECG screening, we hypothesize that an increase in the number of cases will be detected. For sample size estimation consideration, an unpublished, ongoing pilot study conducted in the US estimates the prevalence as 5.3% (3/57) for <=35% and 7% (4/57) for <50%. Sample size estimation is based on a conservative estimate of 4% in the AI-ECG arm. At the alpha=0.05 and 80% power, the sample size is estimated to be 424/group. For the secondary composite endpoint, approximately 5% of the sample is expected to experience hypertensive disorders (Ying, Catov, & Ouyang, 2018). We hypothesize that the addition of AI-ECG will increase the detection of cardiomyopathies and other structural defects of the heart. Accordingly, we assume composite event rates of 5% vs. 10% for the control vs. AI-ECG arm. At 80% power and alpha=0.05, a sample size of 434/group is required. For the final sample size, these estimates are rounded up to 500/group (1000 total) to account for the uncertainties in the calculations. Due to the variability in the occurrence of cardiomyopathy across sites, need to account for study participant withdrawal from the study, no-shows to study visits, and loss to follow up, we plan to enroll 1,400 patients to achieve an accrual target of 1,200 participants while ensuring balanced accrual across all 6 sites.

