7.3.4. Exploratory Hypotheses:	25
7.4. ADDITIONAL STATISTICAL CONSIDERATIONS	26
7.4.1. Handling of Missing Data	26
7.4.2. Multiplicity	26
7.4.3. Interim Analysis	26
7.4.4. Analysis Sets	26
7.4.5. Pre-specified analysis	26
7.5. DEFINITIONS	26
7.6. RECORDING/REPORTING OF ADVERSE EVENTS	27
7.7. STOPPING RULES.....	28
7.8. MEDICAL MONITORING	28
8. DATA HANDLING AND RECORD KEEPING.....	28
8.1. CONFIDENTIALITY	28
8.2. SOURCE DOCUMENTS	28
8.3. CASE REPORT FORMS	29
8.4. RECORDS RETENTION	30
9. STUDY MONITORING, AUDITING, AND INSPECTING	30
9.1. STUDY SITE MONITORING PLAN	30
10. ETHICAL CONSIDERATIONS.....	31
10.1. CONFLICT OF INTEREST.....	31
11. REFERENCES.....	31

Study Summary

Title	Screening for Peripartum Cardiomyopathies using Artificial Intelligence (SPEC-AI) – Nigeria
Running Title	Screening for cardiac dysfunction in pregnancy
Protocol Number	22-000539
Phase	Other
Methodology	Prospective randomized controlled trial
Overall Study Duration	12 months
Subject Participation Duration	Participation will range from a single encounter/visit to a maximum of 12 months
Single or Multi-Site	Multi-Site
Objectives	To determine the effectiveness of an AI-enabled ECG to detect cardiomyopathy and its impact on clinical outcomes in a predominantly Black obstetric population in Nigeria
Number of Subjects	1,400 enrolled / 1,200 accrued
Diagnosis and Main Inclusion Criteria	
The condition being studied is pregnancy related cardiomyopathy
 
Inclusion Criteria:
 
 • Adult female age of 18 – 49 years • Currently pregnant or within 12 months postpartum • Able to provide consent
Study Product, Dose, Route, Regimen	
Intervention: AI algorithm to evaluate electrocardiogram data and generate prediction probabilities for a diagnosis of cardiomyopathy. To be performed intermittently at pre-specified time points during the study
 
Drug, Dose, Route: Not applicable

Statistical Methodology	The analysis plan will focus on comparing AI-ECG algorithm predictions of low ventricular ejection fraction (<50%) with baseline echocardiograms as the reference criterion (clinical standard) and evaluating the impact of AI-ECG screening on maternal outcomes.

1. Introduction

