7.3. Statistical Hypotheses and planned analyses

7.3.1. Descriptive Statistics

Descriptive statistics including measures of central tendency for numeric variables and frequency distributions for categorical variables will be calculated, as appropriate for all variables. Demographic, clinical, and outcome variables (primary and secondary) will be tabulated for all enrolled study participants. These data will be summarized for the entire cohort and stratified by randomized group and region. We will summarize the measures of diagnostic performance (i.e., AUC, sensitivity, specificity) stratified by study entry to account for the differential follow-up testing that may have occurred as a result of the AI-ECG screening

7.3.2. Primary Hypothesis:

AI-ECG is an effective tool to screen for cardiomyopathy, defined as LVEF < 50%, in pregnant women.

Statistical Hypothesis:

- $H_0: P_{\text{ai-ecg}} = P_{\text{control}}$
- $H_A: P_{\text{ai-ecg}} \neq P_{\text{control}}$

Where P defines the proportion of participants that have documented LVEF <50% by the conclusion of the study.

Primary analysis: A chi-square test without continuity correction will be applied to the resulting two by two table (rows: random treatment assignment, columns LVEF < 50% reported by conclusion of the study). The primary analysis will be conducted at the alpha=0.05 level of significance (two-sided).

7.3.3. Secondary Hypotheses:

AI-ECG will provide consistent performance across race, ethnicity, and postpartum enrollment status.

Secondary analysis: The introduction of stratification factors of race, ethnicity and postpartum status (all unique tables) will be used to produce a stratified contingency table. The Breslow-Day test of homogeneity of the odds ratio will be used to test for effect modification (differential treatment effects by strata). There is the potential for sparse strata with this analysis. If the odds ratio is not estimatable due to zero cells, the empirical logit estimator as well as pooled strata (to increase sample size for each strata) will be utilized.

An AI-ECG is an effective tool to screen for cardiomyopathy at different LVEF cut-off values (<45%, <40%, ≤ 35%).

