Secondary analysis: Within the intervention arm that obtains Echos as a part of the study protocol, the AI-ECG model performance will be evaluated. First, the existing algorithm, without retraining, will be used to evaluate discrimination (area under the receiver operating characteristics curve) at various thresholds for LVEF (i.e., 50% as planned for the primary along with 45%, 40% and 35% as noted here). Performance of the model by the patient stratification factors of Age, Race, Ethnicity, and postpartum status will be considered. For these, the reporting standards outlined in the STARD criteria will be adhered to, e.g., inclusion of measures of precision (confidence intervals) and fractional values associated with measures of performance.

7.3.4. Exploratory Hypotheses:

AI-ECG will improve the diagnosis of cardiovascular disease and associated clinical outcomes among pregnant and postpartum women.

Statistical plan: The analysis of this endpoint will use the same techniques as the primary and secondary analyses. Here, a composite score of any cardiovascular disease diagnoses during the course of the study will be utilized as the outcome measure.

An AI-enhanced point of care screening tool using portable, smartphone-compatible ECG devices (AIPOC-ECG) will be effective for the detection of cardiomyopathies among Black pregnant and postpartum women.

Statistical plan: The primary analysis will utilize the predictions based on the clinical 12 lead ECG machine. This exploratory analysis will compare the model performance on the point of care devices with the clinical standard ECG machine.

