7.4. Additional Statistical Considerations

7.4.1. Handling of Missing Data

Missing data may occur throughout the study. The primary analysis, which is based on the AI-ECG prediction for cardiomyopathy is expected to be calculated once digital is received. In the event that the digital ECG file is missing or corrupted, attempts will be made to re-record the ECG. In order to ensure that these repeated ECGs are obtained in a timely fashion, ECGs will be reviewed at the local sites daily and will be transmitted to the coordinating center at Mayo Clinic at the end of every week for additional review. For demographic and medical history data, any missing data will be reported as such in the final analysis.

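### The primary chi-square compares AI-ECG plus universal baseline echocardiography with usual care, so rejecting its null would show case detection by that package, not that the AI-ECG is an effective screening tool

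*Combined protocol and SAP*

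**What the plan says.** **Arms.** Section 3.1 gives the intervention arm AI-ECG cardiomyopathy screening, a baseline echocardiogram and AI-ECG age and sex estimates. Controls get standard of care and the age and sex estimates only. Footnote g of the schedule in section 6.1.2 confirms that the baseline echocardiogram is for the whole intervention arm. After baseline, a newly positive AI-ECG triggers a further echocardiogram in that arm if the baseline one was normal.

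**Primary claim and test.** The primary hypothesis in section 7.3.2 reads "AI-ECG is an effective tool to screen for cardiomyopathy, defined as LVEF < 50%, in pregnant women", in line with the objective in section 2.1. The endpoint in section 7.2.1 is LVEF <50% on echocardiography. For the test, "A chi-square test without continuity correction will be applied to the resulting two by two table", with randomised arm as rows and reported LVEF <50% as columns.

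**Sizing.** On the control arm, section 7.1 states "LVEF<50% is not expected to be diagnosed in the control arm due to the lack of routine echocardiograms". It nevertheless assumes 1% for controls and 4% for the intervention arm. The 4% is presented as conservative beside a pilot prevalence of 7% (4/57).

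**Accuracy.** Section 7.3.3 lists this as secondary: "Within the intervention arm that obtains Echos as a part of the study protocol, the AI-ECG model performance will be evaluated". Its LVEF thresholds include "50% as planned for the primary along with 45%, 40% and 35% as noted here".

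**Other descriptions of the primary analysis.** Section 7.4.1 refers to "The primary analysis, which is based on the AI-ECG prediction for cardiomyopathy". Section 7.3.4 says "The primary analysis will utilize the predictions based on the clinical 12 lead ECG machine". The Study Summary begins its statement of methodology with "The analysis plan will focus on comparing AI-ECG algorithm predictions of low ventricular ejection fraction (<50%) with baseline echocardiograms as the reference criterion", then adds the effect of screening on maternal outcomes as a second aim.

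**The concern.** The arms differ in two ways that bear on the endpoint: the AI-ECG cardiomyopathy result, and an echocardiogram for everyone in one arm. The endpoint can be recorded only by echocardiography. A case found at the baseline echocardiogram counts for the intervention arm whether the AI-ECG flagged it, missed it or was never read. To the extent that cases are found there, rejection does not depend on how well the AI-ECG works. The plan's own reason for expecting no control diagnoses is the absence of routine echocardiography, not the absence of the AI-ECG.

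At stake is the headline conclusion. A significant result could be reported as showing that the AI-ECG screens effectively when the data show only that looking with echocardiography finds more low LVEF than not looking. Two sentences that describe the primary analysis as using AI-ECG predictions make that misreading easier.

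**Working it through.** **Inputs from the documents.** Control rate 1% (or none expected) and intervention rate 4% (section 7.1); two-sided alpha 0.05, uncorrected chi-square (section 7.3.2); 1:1 allocation (section 3.1); 424 per group calculated, 500 after rounding, and 600 per arm from the accrual target of 1,200 (section 7.1); retrospective AUC of 0.92 in pregnant and postpartum women (section 1.1).

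**Assumed, because the documents do not say.** The share of the 4% that the baseline echocardiogram finds: 100%, 75% or 50%. The AI-ECG is taken to have no diagnostic value, so it adds no later cases.

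**Step 1: the plan's sample size.** n = [1.960 × √(2 × 0.025 × 0.975) + 0.842 × √(0.01 × 0.99 + 0.04 × 0.96)]² / 0.03² = (0.4327 + 0.1850)² / 0.0009 = 423.97, so 424 per group. The arithmetic is right; the issue is what is compared.

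**Step 2: rejection with a worthless AI-ECG.** Let T and C be the case counts in the two arms, each binomial with n participants, and m = T + C. The uncorrected statistic is (T − C)² × 2n / [m(2n − m)]. Sum the joint probabilities of all pairs with a statistic of at least 3.841 and T > C.

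| Share of the 4% found at baseline | Intervention rate | Per arm | Controls 1% | Controls 0% |
|---|---|---|---|---|
| 100% | 4% | 424 | 83% | >99.9% |
| 100% | 4% | 500 | 89% | >99.9% |
| 100% | 4% | 600 | 94% | >99.9% |
| 75% | 3% | 600 | 72% | >99.9% |
| 50% | 2% | 600 | 29% | 99.8% |

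The last two rows count the baseline echocardiogram alone. If the remaining cases were instead diagnosed clinically at the control ratio (1 in 4), the intervention rates would be 3% + 0.25 × 1% = 3.25% and 2% + 0.25 × 2% = 2.5%. Rejection against 1% would then be 80% and 52%.

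**Step 3: the plan's own control expectation.** With no control cases, four intervention cases suffice: 16 × 1200 / (4 × 1196) = 4.01 at 600 per arm, above 3.841. Three do not: 9 × 1200 / (3 × 1197) = 3.01.

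**Step 4: what the accuracy analysis can tell.** Hanley-McNeil variance for AUC A, with m cases and n non-cases: [A(1 − A) + (m − 1)(Q₁ − A²) + (n − 1)(Q₂ − A²)] / (mn), where Q₁ = A/(2 − A) and Q₂ = 2A²/(1 + A). Take 600 intervention participants.

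- 24 baseline cases (4%): AUC 0.92 has SE 0.038 and lower 95% limit 0.84; AUC 0.50 has upper limit 0.62.
- 12 baseline cases (2%): AUC 0.92 has SE 0.054 and lower limit 0.81; AUC 0.50 has upper limit 0.67.

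These normal limits are rough with so few cases, but they separate a useful AI-ECG from a useless one. The chi-square cannot do so for cases found at baseline.

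**Step 5: the texts side by side.** Sections 7.2.1, 7.3.2 and 7.1 agree on one endpoint, one test and one sample size, with no AI-ECG prediction. Section 7.4.1 says that the primary analysis is based on the prediction, and section 7.3.4 says that it uses the predictions. Neither is true of the chi-square. The 50% remark in section 7.3.3 may mean only the primary LVEF threshold. The Study Summary names accuracy first and outcomes second, and does not say which is primary.

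**The case against.** **It is a legitimate trial of a package.** This stands. Section 3.1 states the package openly, improved detection is a listed objective (section 2.2), and the chi-square tests package against usual care validly. A reader might infer that the randomised comparison is invalid, or that the AI-ECG has no part in it. The documents support neither: triggered echocardiograms can add later cases, and controls may have clinically indicated echocardiograms. What the test cannot do is separate triggered cases from those found by universal baseline imaging.

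**The 94% assumes the extreme.** This also stands. Women may enter in the first trimester, so some cases may arise after baseline, and with half found there the figure is 29% against 1% controls. The range has to be read with its assumption.

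**Accuracy is already planned.** Yes, with confidence intervals and STARD reporting, against an echocardiogram that everyone in the arm has at baseline. Section 7.3.1 also stratifies accuracy by study entry to allow for differential follow-up testing. That does not address the difference in echocardiography between arms, and the primary hypothesis still attaches the screening claim to the chi-square.

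**The plan does fix its primary analysis.** Largely true. A reader might infer that the primary analysis is undefined and could be chosen after the data are seen. Sections 7.2.1 and 7.3.2 are too explicit for that. Two sentences are wrong and two are ambiguous.

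**Conclusion.** The concern holds as a mismatch between test and claim. The primary chi-square can establish more case detection under AI-ECG plus universal baseline echocardiography than under usual care. It cannot establish that the AI-ECG is an effective screening tool.

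The size depends on how much of the assumed 4% the baseline echocardiogram finds, which the documents do not give. For the shares examined, rejection with a worthless AI-ECG at 600 per arm runs from 29% to 94% against 1% controls and exceeds 99% against none. The structural point needs none of these figures: it follows from who is imaged and what enters the table.

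A reader might also infer that accuracy must become a primary or co-primary endpoint. The documents do not compel that. Restating the randomised claim and resting the screening claim on the planned accuracy analysis removes the inferential error.

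**What to change.** 1. Keep the chi-square and its event definition. In sections 7.1 and 7.3.2, restate the hypothesis, the conclusion it supports and the power statement as detection of LVEF <50% under AI-ECG plus universal baseline echocardiography versus usual care.
2. State that the screening claim rests on the planned intervention-arm accuracy analysis at LVEF <50%: AUC, sensitivity and specificity with 95% confidence intervals, pairing the baseline 12-lead AI-ECG with the baseline echocardiogram. Fix the AI-ECG cut-off before data are seen. None appears in the available text; the detailed SAP promised in section 7.4.5 could hold it.
3. Correct sections 7.4.1 and 7.3.4, and clarify section 7.3.3 and the Study Summary, to match sections 7.2.1 and 7.3.2.

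**Cost.** No new tests, visits or participants, and no change to the randomised comparison; the revised text needs submission to the local review boards as an amendment. The randomised result supports a narrower claim. Accuracy will be imprecise if cases are few: sensitivity of 22/24 has an exact 95% interval of 73–99%, and 11/12 has 62–100%.

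**Optional, for the sponsor to decide.** Accuracy could be made co-primary with a pre-set success limit, which would narrow the route to a positive trial and need its own sample-size justification. Echocardiography utilisation (secondary in section 7.2.2, exploratory in section 2.3) could be reported excluding protocol baseline and end-of-study echocardiograms. That reduces the imbalance between arms but does not remove it, since a known baseline LVEF may change later ordering in one arm only.
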